#### 6 STUDY DESIGN AND ENDPOINTS

## 6.1 Overall Study Design

The proposed phase I/IIa clinical trial is an open-label trial where subjects will take part in a single injection study of self-complementary AAV9 carrying the ACCA snRNA under the control of a U7 promoter (scAAV9.U7.ACCA) delivered one time through a peripheral vein of the DMD subjects.

The comparison of muscle tissue from baseline and 90 days post-gene transfer will be the basis of the secondary efficacy analysis. Upon completion of the 2-year study period, subjects will be monitored annually as per standard of care for up to 5 years.

There will be at least 6 weeks between dosing of the first and second subjects within the cohort. The allowance of 6 weeks between dosing of the first and second subjects in the cohort provides time for an DSMB review of the safety analysis from five time points (Days 1, 2, 7, 14 and 30) prior to dosing of the next subject.

Notably, we have not required a 30 day time point between subsequent subjects because we wish to accommodate the realistic possibility that siblings may both enroll in the study, and viral shedding might possibly expose the second of each sibling pair to the vector, generating antibodies that are exclusionary to the trial. We would consider the burden on families of living apart for six weeks to be excessive, and the prospect of making parents choose between one or another of their sons to enroll to be ethically untenable.

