## 6.3 Number of Subjects

Up to 3 DMD subjects matching the inclusion/exclusion criteria will be enrolled. Enrollment will be proceed as outlined in Section 6.4.

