## 6.4 Dosing plan

The proposed phase I/IIa clinical trial is an open-label single injection study of systemic (intravenous) delivery of scAAV9.U7.ACCA for DMD subjects with associated duplications of exon 2 in the DMD gene. Preclinical data shows that the small nuclear RNA (snRNA) construct delivered by the scAAV9.U7.ACCA vector causes significant skipping of exon 2, resulting in

exclusion of one (wild type) or both copies (Del2) of the exon from the mature messenger RNA (mRNA) with a high degree of efficiency. Translation of either the wild-type mRNA or N-truncated mRNA (via IRES translational initiation) results in a highly functional isoform. The dose selection is based on toxicology-biodistribution studies and predicted by pre-clinical studies in non-human primates.

This protocol is designed to deliver the vector via a one-time infusion through a peripheral vein of the DMD subjects. The subjects will receive the minimal efficacious dose (3 x  $10^{13}$  vg/kg) as identified in murine studies. The total vector genome dose for subjects who weigh  $\geq 20$ kg will be adjusted by rounding the subject body weight up to the closest whole kilogram. The total vector genome dose for subjects who weigh <20kg will be adjusted by rounding the subject body weight to the nearest tenth of a kilogram.

Dose (vg/kg)	N
$3.0 \times 10^{13}$	1-3

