## 6.5 Criteria for Study Termination

An independent Data Safety Monitoring Board (DSMB) will be established. Safety data will be monitored on a continual basis throughout the trial. The DSMB can recommend early termination of the trial for reasons of safety. Study enrollment will be halted by the investigators when any subject experiences two or more Grade 3, or higher adverse events that are **unanticipated** and **possibly, probably, or definitely related** to the study drug. This will include any subject death, important clinical laboratory finding, or any severe local complication in the injected area related to administration of the study agent. If after review by the DSMB, the decision is made to continue, the study will proceed according to Section 6.4 of this protocol.

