## 9.1 Study Visits

### 9.1.1 Screening (day -45 to day -1)

Informed consent will be obtained prior to the collection of any data and any study related procedures. Baseline measures from subjects will be obtained prior to gene transfer and will occur over two visits (up to 3 weeks apart). Because a pre-existing antibody response would be exclusionary, ELISA and ELISpot testing will be performed at the first visit, allowing the results to be reviewed prior to the open muscle biopsy and its subsequent risks (including sedation). The weight obtained at screening will be used to calculate the viral vector dose.

The following assessments will occur at these visits:

- Informed Consent
- Assent, if applicable
- Medical history
- Concomitant Medications
- Physical Exam
- Vital Signs (temperature, respiratory rate, heart rate, blood pressure, height (see Section 10.5 for more details), and weight)
- MRI of the lower legs (see Section 10.2 for more details)
- ECHO
- ECG
- Functional tests (variable depending on age of enrollment)
  - Enrollment age:  $\leq$  36 months
    - Bayley-IV scores (Bayley Scales of Infant and Toddler Development)
  - o Enrollment age: > 36 months and < 5 years of age
    - North Star Ambulatory Assessment (NSAA)

- Time to climb four stairs
- Amount of time required to walk 100 meters (100MWT)
- Enrollment age:  $\geq$  5 years old until Non-Ambulant
  - North Star Ambulatory Assessment (NSAA) score
  - Time to climb four stairs
  - Amount of time required to walk 100 meters (100MWT)
  - Force generated in knee flexion and extension in maximum voluntary isometric contraction (MVICT).
- Pulmonary functional tests (PFTs), including forced vital capacity. (See Section 10.3 for more details.)
- Open Muscle Biopsy (For details, see Section 10.2)

The following blood lab work will occur at this visit. (Lab work may be drawn over several days during visit if deemed necessary by study team except as noted above for ELISA and ELISpot.)

- Complete blood cell count (CBC) and differential, platelets
- Aspartate aminotransferase (AST)/alanine transaminase (ALT)
- Gamma-glutamyl transpeptidase (GGT)\*
- A Comprehensive Metabolic Panel (CMP) that includes:
  - Albumin/Serum total protein
  - Serum total bilirubin
  - Electrolytes
  - o Calcium
  - o Creatinine/Blood Urea Nitrogen (BUN)
  - Serum glucose
  - Alkaline phosphatase
- Prothrombin time (PT)/activated partial thromboplastin time (PTT)/INR
- Amylase
- Creatine kinase (CK)
- Cystatin C

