#### 9.1.2 Gene Transfer Visit

#### 9.1.2.1 Pre Infusion Visit (Day -1)

Subjects will arrive at the Nationwide Children's Hospital within 24 hours prior to gene transfer.

The following assessments will occur at this visit:

- Medical history
- Concomitant Medications
- Adverse Events
- Physical Exam
- Vital Signs (heart rate, respiratory rate, temperature, blood pressure, height (see Section 10.5 for more details) and weight)

The following blood lab work will occur at this visit:

- Complete blood cell count (CBC) and differential, platelets
- Aspartate aminotransferase (AST)/alanine transaminase (ALT)
- Gamma-glutamyl transpeptidase (GGT)\*
- A Comprehensive Metabolic Panel (CMP) that includes:
  - o Albumin/Serum total protein
  - o Serum total bilirubin
  - Electrolytes
  - o Calcium
  - o Creatinine/Blood Urea Nitrogen (BUN)
  - o Serum glucose
  - Alkaline phosphatase
- Prothrombin time (PT)/activated partial thromboplastin time (PTT)/INR
- Creatine kinase (CK)
- Direct Bilirubin
- ELISpots for T-cell responses to AAV9 and Dystrophin
- Whole blood for biobanking

In previous gene therapy studies at NCH, there has been an observed antigen specific T-cell response to the AAV vectors. This is an expected response between 2 - 4 weeks following gene transfer. One possible consequence to such antigen specific T-cell responses is clearance of the transduced cells and loss of transgene expression. All subjects (ages 4 years and older) will already be on prednisone, prednisolone, or deflazacort for 12 weeks at time of enrollment as part of the inclusion criteria. The standard clinical dose of prednisone or prednisolone is 0.75 mg/kg/day, and the standard clinical dose of deflazacort is 0.9 mg/kg/day. In order to dampen the host immune response to our AAV-based therapy, for each subject the glucocorticoid dose will be increased to prednisone or prednisolone 1.0 mg/kg/day, not to exceed 60 mg/day; subjects on deflazacort at enrollment will be placed on prednisone or prednisolone for the immediate perinijection period. For subjects younger than 4 years of age who may not be on a corticosteroid,

\* For subjects taking drugs that potentially induce GGT synthesis through the cytochrome P450 system, the clinically significant range will be estimated starting at two times the levels obtained from the baseline screening test and up.

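### Section 6.1 waives the 30-day time point between subjects 2 and 3 for a reason that applies only to siblings, but the waiver covers any third subject

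*Combined protocol and SAP*

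**What the plan says.** Section 6.1 deals with the two possible intervals differently. For the first it states: "There will be at least 6 weeks between dosing of the first and second subjects within the cohort". The purpose given is DSMB review of five time points (Days 1, 2, 7, 14 and 30) before the next dosing. For later dosings it states: "we have not required a 30 day time point between subsequent subjects". The reason is that brothers may both enroll and that "viral shedding might possibly expose the second of each sibling pair to the vector", leaving him with antibodies that exclude him. The section adds that six weeks of living apart, or a choice between sons, would be too much to ask of a family.

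Section 6.3 caps the trial: "Up to 3 DMD subjects matching the inclusion/exclusion criteria will be enrolled". It refers to Section 6.4 for how enrollment proceeds. Section 6.4 gives the single dose and the weight-rounding rule ("The subjects will receive the minimal efficacious dose") but no dosing interval. Section 12.1.3 schedules a DSMB meeting before the study starts, one after subject 1's Day 30 visit, and then meetings about six-monthly or on request.

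Several safeguards apply to every subject:

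- Sections 6.5 and 11.5: "Safety data will be monitored on a continual basis throughout the trial".
- Section 11.3.2: life-threatening SAEs and DLTs go to the DSMB within 48 hours.
- Section 11.5: investigators consult the DSMB on every related Grade 3 or higher event before enrollment goes on. Enrollment halts if one subject has two or more such events that are unexpected.
- Section 11.4: the investigator consults the DSMB and FDA before enrollment resumes.

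**The concern.** The exception is wider than its reason. Shedding within a household can cost a brother his eligibility, but it does not affect a boy from another family. For a third boy with no brother in the trial, Section 6.1 removes the Day 30 safeguard and offers nothing in return.

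The remaining safeguards are mostly event-driven, so they can act only once subject 2's event has appeared. Section 9.1.2.1 says of the T-cell response to the vector: "This is an expected response between 2 - 4 weeks following gene transfer". Section 11.4.2 expects falls in leukocytes and lymphocytes within the first 30 days, and Section 10.6.1 bases the steroid decision on the 30-day ELISpot result. If subject 3 is infused soon after subject 2, much of what the protocol expects to happen in subject 2 has not happened yet.

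Safety is the primary outcome, and a single infusion cannot be taken back. Subject 1 may also be a limited guide to the next boy. Eligibility runs from 6 months to under 14 years, and boys under 4 may start steroids only on Day -1, whereas older boys have had at least 12 weeks of them.

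**Working it through.** **Step 1. Reproduce the plan's own interval (subject 1 to subject 2).** Inputs: 6 weeks = 42 days (6.1); Day 30 visit with a window of 3 days either way, so Day 27 to Day 33 (9.1.3.3). Time left for DSMB review = 42 − visit day.

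- Visit on Day 27: 42 − 27 = 15 days
- Visit on Day 30: 42 − 30 = 12 days
- Visit on Day 33: 42 − 33 = 9 days

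The 6-week figure does what Section 6.1 says it does.

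**Step 2. Find which interval is waived.** With at most three subjects (6.3) there are two intervals. The first is set at 42 days, so the waiver applies to subject 2 to subject 3 alone. Sections 6.1, 6.3, 6.4 and 12.1.3 set no minimum for it.

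**Step 3. Count what is known about subject 2 when subject 3 is dosed.** Nominal visit days; g = days between the two dosings.

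| g (days) | Subject 2 time points reached | Count of 5 |
|---|---|---|
| 0 | none | 0 |
| 1 | Day 1 | 1 |
| 2–6 | Days 1, 2 | 2 |
| 7–13 | Days 1, 2, 7 | 3 |
| 14–29 | Days 1, 2, 7, 14 | 4 |
| 30 or more | all | 5 |

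The T-cell window of 2 to 4 weeks is Days 14 to 28. A gap under 14 days ends before that window opens in subject 2, and a gap under 28 days ends before it closes. Subject 1's five time points are available at any g.

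**Step 4. See whether the DSMB calendar fills the gap.** Section 12.1.3 ties one meeting to subject 1's Day 30 visit and spaces the rest about 6 months apart, taken here as 180 days. Suppose that meeting falls between days 30 and 42 after subject 1's dosing, and subject 2 is dosed at the earliest date, day 42.

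- Next routine meeting: 30 + 180 = day 210, to 42 + 180 = day 222
- Measured from subject 2's dosing: 210 − 42 = 168 days, to 222 − 42 = 180 days

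That is about 5.5 to 6 months after subject 2's dosing. If subject 2 is dosed later, a routine meeting could fall in the gap, but nothing requires it.

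**Step 5. Illustrate what a second observed child adds.** The documents give no toxicity rate, so assume a chance p per child of a toxicity visible by Day 30, independent between children. The chance of having seen at least one is p with one child observed and 1 − (1 − p)² with two.

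| Assumed p | One child | Two children |
|---|---|---|
| 10% | 10% | 19% |
| 20% | 20% | 36% |
| 30% | 30% | 51% |
| 50% | 50% | 75% |

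**The case against.** The strongest reply is that this is a deliberate, disclosed choice with an ethical reason, in a trial with one dose level and no escalation. Subject 1 is a same-dose sentinel whose five time points are reviewed before anyone else is treated, and no document asks for a second sentinel. This stands as a defense of the waiver for brothers. It does not explain why the waiver extends to boys whom the reason does not reach.

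A reader might infer that the DSMB need not see subject 2's data at all before subject 3 is dosed. The documents do not support that. Section 11.5 requires consultation on any related Grade 3 or higher event, expected or not; Section 11.4 adds FDA; Section 11.3.2 sets the 48-hour report; and the DSMB can ask for a meeting. What is missing is a scheduled review when no such event has yet appeared.

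A reader might also infer that close dosing is intended, or that a T-cell response in subject 2 would stop subject 3. Neither is in the text. No section plans a short gap. The T-cell response is expected, the consequence named is loss of transduced cells and expression, and it is managed with steroids guided by ELISpot. It triggers no hold by itself. Its relevance is only that Day 30 is when the protocol itself takes stock.

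Finally, limiting the waiver to subject 2's brother would be wrong. Subject 1's brother, if dosed third, can now follow subject 2 at once, and the shedding reason covers him equally. Any fix has to keep that.

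**Conclusion.** The point holds as a cheap improvement. For a subject 3 with no brother already in the trial, the required minimum after subject 2 is 0 days, against 42 days between subjects 1 and 2. Before his dosing the protocol guarantees 0 of subject 2's 5 time points, and no scheduled DSMB review of subject 2 is required unless a related Grade 3 or higher event has already occurred.

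The scope is small: one interval, at most one of three children, no effect at N = 1 or 2, and no endpoint or analysis changed. The conclusion rests on the text of Sections 6.1, 6.3, 6.4, 11.4, 11.5 and 12.1.3. The DSMB timing in Step 4 depends on reading the six-monthly interval as 180 days and on dosing subject 2 near week 6. The percentages in Step 5 are illustrative only.

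**What to change.** In Section 6.1, limit the waiver to a subject 3 who is a sibling of any previously dosed subject. For any other subject 3, require DSMB review of subject 2's safety data through Day 30 before dosing; the same 6-week allowance would serve. Add that review to the meeting schedule in Section 12.1.3.

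The cost is about one sentence in each section and one extra DSMB review. At most one boy waits: about 30 to 33 days plus review time, or 42 days in total under the 6-week allowance. He would face a delay that a sibling in the same slot would not. His screening need not be repeated if it is scheduled with this in mind. The window in Section 9.1.1 opens 45 days before dosing, so with dosing 42 days after subject 2 it opens 45 − 42 = 3 days before subject 2's infusion. Brothers of either earlier subject keep exactly what the protocol now gives them.

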## **6.2** Study Population

All subjects will be enrolled at Nationwide Children's Hospital.

DMD subjects aged between 6 months and less than 14 years of age, with proven exon 2 duplication mutations of the DMD gene, will be eligible for enrollment in the gene transfer study. Subjects of any ethnic or racial background will be enrolled.

## 6.3 Number of Subjects

Up to 3 DMD subjects matching the inclusion/exclusion criteria will be enrolled. Enrollment will be proceed as outlined in Section 6.4.

## 6.4 Dosing plan

The proposed phase I/IIa clinical trial is an open-label single injection study of systemic (intravenous) delivery of scAAV9.U7.ACCA for DMD subjects with associated duplications of exon 2 in the DMD gene. Preclinical data shows that the small nuclear RNA (snRNA) construct delivered by the scAAV9.U7.ACCA vector causes significant skipping of exon 2, resulting in

exclusion of one (wild type) or both copies (Del2) of the exon from the mature messenger RNA (mRNA) with a high degree of efficiency. Translation of either the wild-type mRNA or N-truncated mRNA (via IRES translational initiation) results in a highly functional isoform. The dose selection is based on toxicology-biodistribution studies and predicted by pre-clinical studies in non-human primates.

This protocol is designed to deliver the vector via a one-time infusion through a peripheral vein of the DMD subjects. The subjects will receive the minimal efficacious dose (3 x  $10^{13}$  vg/kg) as identified in murine studies. The total vector genome dose for subjects who weigh  $\geq 20$ kg will be adjusted by rounding the subject body weight up to the closest whole kilogram. The total vector genome dose for subjects who weigh <20kg will be adjusted by rounding the subject body weight to the nearest tenth of a kilogram.

Dose (vg/kg)	N
$3.0 \times 10^{13}$	1-3

## 6.5 Criteria for Study Termination

An independent Data Safety Monitoring Board (DSMB) will be established. Safety data will be monitored on a continual basis throughout the trial. The DSMB can recommend early termination of the trial for reasons of safety. Study enrollment will be halted by the investigators when any subject experiences two or more Grade 3, or higher adverse events that are **unanticipated** and **possibly, probably, or definitely related** to the study drug. This will include any subject death, important clinical laboratory finding, or any severe local complication in the injected area related to administration of the study agent. If after review by the DSMB, the decision is made to continue, the study will proceed according to Section 6.4 of this protocol.

## 6.6 Establish Subject Identification Number

All subjects will be given a unique sequentially assigned subject number. Subjects will be identified by code only to protect identity. This will be done prior to any research procedures when the subject is identified as a potential candidate.

The subject identification number will be generated as described below:

- 1) U7 (study identifier)
- 2) DUP2 (to indicate a DMD gene transfer trial)
- 3) The last two digits will represent the sequential number of candidates screened

Example: Subject ID: U7-DUP2-01

#### 7 STUDY ENROLLMENT AND WITHDRAWAL

All subjects will be enrolled at Nationwide Children's Hospital. Subjects will be identified from among the muscular dystrophy clinic population, as well as among a large number of treatment-amenable subjects who have self-identified themselves to the investigators.

#### 7.1 Inclusion/Exclusion

Inclusion Criteria

- 1. Age greater than 6 months and less than 14 years.
- 2. Confirmed duplication of exon 2 the DMD gene using a clinically accepted technique that completely defines the mutation.
- 3. Pre-ambulant (not yet walking) or ambulant (as defined by the ability to walk 10 meters without assistance).
- 4. Males of any ethnic group will be eligible
- 5. Ability to cooperate with muscle testing.
- 6. In subjects age 4 and above, stable dose and regimen of corticosteroid therapy (including either prednisone or deflazacort and their generic forms) for at least 12 weeks prior to gene transfer.

#### Exclusion Criteria

- 1. Active viral infection based on clinical observations.
- 2. Symptoms or signs of cardiomyopathy, including:
  - a. Dyspnea on exertion, pedal edema, shortness of breath upon lying flat, or rales at the base of the lungs
  - b. Echocardiogram with ejection fraction below 40%
- 3. Serological evidence of HIV infection, or Hepatitis B or C infection
- 4. Diagnosis of (or ongoing treatment for) an autoimmune disease
- 5. Persistent leukopenia or leukocytosis (WBC  $\leq$  3.5 K/ $\mu$ L or  $\geq$  20.0 K/ $\mu$ L) or an absolute neutrophil count < 1.5K/ $\mu$ L
- 6. Concomitant illness or requirement for chronic drug treatment that in the opinion of the SI creates unnecessary risks for gene transfer
- 7. AAV9 binding antibody titers  $\geq 1:400$  as determined by ELISA immunoassay
- 8. Abnormal laboratory values in the clinically significant range in Table 7, based upon normal values in the Nationwide Children's Hospital Laboratory

Table 7: Normal and abnormal laboratory values at Nationwide Children's Hospital Laboratory

System	Assay	Normal Range	Abnormal (Clinically Significant)
Liver Function	GGT	8-80 U/L	>80 U/L
	Total Bilirubin	0.1-1 mg/dL	≥3 mg/dL
	Direct Bilirubin	<0.6 mg/dL	>2 mg/dL
Renal Function	Cystatin C	0.3-1.3 mg/dL	>1.8 mg/dL
Hematologic Hemoglobin		(g/dL) 2 – 6 yrs: 11.5-13.5 6 – 12 yrs: 11.5-15.5	For all ages: $\leq 8 \text{ or } \geq 18 \text{ g/dL}$
		13-18 years: 13-15	-

Hematologic	White Blood Cells	4 – 6 yrs: 5.5-15.5 6 – 10 yrs: 5-14.5 10 – 21 yrs: 4.5-13.5	For all ages: White blood cell count $\leq 3.5 \text{ or } \geq 20 \text{ x } 10^3$ cells/mL OR Absolute neutrophil count of $\leq 1.5 \text{ x } 10^3 \text{ cells/mL}$
-------------	----------------------	--	--

\* For Hemoglobin, subjects will be excluded if they have a value less than the lower limit of normal for age at screening regardless of age. Abnormal but not clinically significant hemoglobin levels may be repeated during the screening period, and the subject accepted for enrollment if the results are not less than the lower limit of normal.

## 7.2 Subject Withdrawal Criteria

If a subject chooses to withdraw at any point BEFORE gene transfer, no further follow up will be required, other than routine post-operative care if a muscle biopsy was completed.

If a subject chooses to withdraw at any point AFTER gene transfer, all safety laboratory studies will still need to be completed. The subject will not be required to undergo any further muscle biopsies, muscle MRIs (if applicable) or functional assessments.

